5 STUDY POPULATION

Potential study participants may be identified and recruited into the study through various methods, such as:

- Database of individuals who have agreed to be contacted for future studies;
- In-person recruitment;
- Physician to physician referrals;
- Internet advertisement;
- Print advertisement.

Note that scripts and advertisement fliers will be submitted to the IRB as necessary.

5.1 Inclusion Criteria

1. Outpatient, male or female of any race, 18 years of age or older. Female subjects of childbearing potential must have a negative UPT at Baseline.

A female is considered of childbearing potential unless she is:

 - *postmenopausal for at least 12 months prior to study device administration;*
 - *without a uterus and/or both ovaries; or*
 - *has been surgically sterile for at least 6 months prior to study device administration.*
2. Diagnosed with facial acne vulgaris.
3. At least one (1) identifiable inflammatory lesion that, in the opinion of the investigator, is clinically indicated for indicated for standard-of-care intralesional injection(s) of triamcinolone and for which the research participant has already agreed to have standard-of-care intralesional injection(s) of triamcinolone.
4. Able to follow study instructions and likely to complete all required visits.
5. In good general health as determined by medical history at the time of screening (Investigator discretion).
6. Sign the IRB-approved ICF (including HIPAA authorization) prior to any study-related procedures being performed.

5.2 Exclusion Criteria

1. Female subjects who are pregnant or breast-feeding.
2. Known hypersensitivity or previous allergic reaction to any constituent of triamcinolone injection.
3. Active cutaneous viral infection in any treatment area at Baseline.

Clinical Trial Protocol ATM-2201	Version 2.0 28-Oct-2022	Confidential Page 11/25
-------------------------------------	----------------------------	----------------------------

4. Have concomitant skin disease or infection (other than acne) or presence of skin comorbidities in the areas of skin where study device will be used.
5. History of poor cooperation or unreliability (Investigator discretion).
6. Planning to move out of the area prior to study completion.
7. Subjects who are investigational site staff members or family members of such employees.
8. Exposure to any other investigational /device within 30 days prior to Visit 1.

5.3 Subject Withdrawal

Subjects are free to withdraw from participating in this study at any time and for whatever reason, specified or unspecified, and without prejudice. All premature discontinuations and their reasons must be carefully documented by the PI in the source documents, CRF, and (if applicable), on the AE form.

6 SUBJECT NUMBERING, RANDOMIZATION AND BLINDING

This is an open-label, non-randomized, single-group study. All subjects who are enrolled will receive treatment with the study device. Randomization and blinding are not applicable.

All enrolled subjects will receive a 3-digit subject number, starting at 001. Subject numbers will be assigned in ascending order. The subject number will be used to identify the subject throughout the study. Subjects withdrawn from the study will retain their subject number; new subjects will be allocated a new subject number. Screen Failures will not be entered in the eCRF.

7 CONCOMITANT AND PROHIBITED MEDICATION/PROCEDURES

7.1 Concomitant Medications and Procedures

All treatment/procedures received by the subject throughout the treatment period, including the name of the treatment/procedure, must be recorded in the CRF with end dates, if applicable. Every attempt should be made to keep concomitant therapy dosing constant during the study. Any change to concomitant therapy should be noted in source documents and the CRF.

There are no prohibited medications defined for the study. Any necessary therapies that are deemed appropriate by the Investigator are permitted. Subjects currently taking medications to treat acne should be instructed to maintain their current dosing throughout the study.

8 INVESTIGATIONAL PRODUCT MANAGEMENT

8.1 Intradermal Needle Adapter

The intradermal needle adapter is an accessory that slips on the end of a standard 32G 0.5" needle and reduces the effective length of the needle to 1mm (Figure 1). The adapter is made of biocompatible 304 Stainless Steel. It is packaged in single use bags and will be autoclaved or prepared in the standard manner for typical stainless steel instruments used by the Investigator.

Figure 1. Intradermal Needle Adapter

8.2 Triamcinolone for Injection

A commercial supply of triamcinolone 10% for injection will be provided to the site and diluted with Saline to the appropriate concentration. The site will store triamcinolone as per the conditions described in the package insert.

A standard 32G 0.5" needle will be fixed to a 1.0 mL luer syringe and the syringe will be loaded with an appropriate volume and concentration of triamcinolone. A total of 0.05 mL to 0.15 mL of triamcinolone 0.5% to 2.5% will be injected into each target lesion. The choice of volume and concentration for each individual lesion will be at the discretion of the Investigator as per his clinical judgement. The intradermal needle adapter will then be installed on the needle.

At least one (1), and up to three (3) inflammatory target lesions will be selected for intralesional injections of triamcinolone using the intradermal needle adapter.

9 STUDY EVALUATIONS

9.1 Visit Procedures

9.1.1 Visit 1 (Baseline; Day 1)

- Written informed consent (incl. HIPAA and California Bill of Rights)
- Inclusion / exclusion criteria
- UPT (if female subject of childbearing potential)
- Medical history and demographics
- Concomitant medications/treatments
- Investigator Assessments
 - *Global Severity Score (GSS)*
 - *Target Lesion Assessments: lesion erythema, lesion severity*
 - *Target Lesion Photography (pre- and post-injection)*
 - *Target Lesion Injection Videography*
- Subject Assessments
 - *Target lesion pain (pre-injection)*
 - *Intralesional injection pain (post-injection)*
- Intralesional injection(s)
- AE Assessment

Clinical Trial Protocol ATM-2201	Version 2.0 28-Oct-2022	Confidential Page 13/25
-------------------------------------	----------------------------	----------------------------

9.1.2 Visits 2 to 6 (24hr, 48hr, 72hr, 7 days±1 day, 14 days±2 days)

- Investigator Assessments
 - *Target Lesion Assessments: lesion erythema, lesion severity, improvement*
 - *Target Lesion Photography*
- Subject Assessments
 - *Target lesion pain*
 - *Subject Satisfaction*
- Concomitant medications/treatments
- AE Assessment

9.2 Investigator Assessments

9.2.1 Global Severity Score (GSS)

The Investigator will use the following GSS scale to determine subjects' Baseline acne severity (Table 1).

Table 1: Global Severity Score

Score	Grade	Description
0	Clear	Normal, clear skin with no evidence of acne vulgaris
1	Almost Clear	Rare non-inflammatory lesions present, with rare non-inflamed papules (papules must be resolving and may be hyperpigmented, though not pink-red)
2	Mild	Some non-inflammatory lesions are present, with few inflammatory lesions (papules/pustules only; no nodulocystic lesions)
3	Moderate	Non-inflammatory lesions predominate, with multiple inflammatory lesions evident: several to many comedones and papules/pustules, and there may or may not be one nodulocystic lesion
4	Severe	Inflammatory lesions are more apparent, many comedones and papules/pustules, there may or may not be up to 2 nodulocystic lesions

9.2.2 Target Lesion Assessments

Up to 3 inflammatory lesions on the face will be chosen for intralesional injections of triamcinolone using the study device as per Section 8 (i.e., target lesions).

Each injected lesion will be individually assessed as per the following methods.

9.2.2.1 Target Lesion Erythema

The Investigator will use the following scale to determine the severity of erythema for each target lesion (Table 2).

Table 2: Target Lesion Erythema

Grade	Description
0	No Erythema
1	Mild Erythema
2	Moderate Erythema
3	Severe Erythema
4	Very Severe Erythema

Clinical Trial Protocol ATM-2201	Version 2.0 28-Oct-2022	Confidential Page 14/25
-------------------------------------	----------------------------	----------------------------

9.2.2.2 Target Lesion Severity

The Investigator will determine the severity of each target lesion as per the scale in Table 3.

Table 3: Target Lesion Severity

Grade	Description
0	None
1	Mild
2	Moderate
3	Severe
4	Very Severe

9.2.2.3 Target Lesion Improvement

The Investigator will determine the improvement seen with each target lesion as per the scale in Table 4. Lesion improvement will not be assessed at Baseline.

Table 4: Target Lesion Improvement

Grade	Description
1	Clear (100%)
2	Almost clear (90% to <100%)
3	Marked improvement (75% to <90%)
4	Moderate improvement (50% to <75%)
5	Fair improvement (25% to <50%)
6	No change
7	Worse

9.2.2.4 Target Lesion Videography

A video will be taken of each injected lesion starting from just prior to needle penetration and up to 10 seconds after removed of needle from lesion.

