Investigator Assessments	
 Global Severity Score (GSS): A 5-point scale assessing ranging from 0 (Clear) to 4 (Severe). Note: only Baseline assessments will be conducted. Target Lesion Erythema: A 5-point scale ranging from 0 (No Erythema) to 4 (Very Severe Erythema). Target Lesion Severity: A 5-point scale ranging from 0 (None) to 4 (Very Severe). Target Lesion Improvement: A 7-point scale ranging from 1 (Clear; 100%) to 7 (Worse). Target Lesion Videography: A video will be taken of each injected lesion starting from just prior to needle penetration and up to 10 seconds after removed of needle from lesion. Target Lesion Photography: Photographs will be taken at each study visit of each injected inflammatory lesion. At Baseline, photographs will be taken both pre- and post-injection.
Subject Assessments	
 Target Lesion Pain: Target lesion pain will be self-assessed by the subject using a Visual Analog Scale Intralesional Injection Pain: Target lesion injection pain will be self-assessed by the subject using a Visual Analog Scale. Subject Satisfaction: A 5-point scale ranging from 1 (Very satisfied) to 4 (Very dissatisfied).
Safety Endpoints	Adverse Events
Sample Size	Approximately 20 subjects will be enrolled. This is a POC study and a formal sample size justification is not provided for this study. It is the opinion of the Sponsor that a total of 20 subjects will be sufficient to achieve the objective of the study.
Statistical Methods	
For categorical parameters, the number and percentage of subjects/observations in each category will be presented. The denominator will be based on the number of subjects/observations appropriate for the purpose of analysis. For continuous parameters, descriptive statistics will include n (number of subjects or observations), mean, standard deviation, median, and range. Two-sided 95% CIs will be provided for all study outcomes.
 
The modified Intent-to-Treat (mITT) Population (defined as all subjects who were enrolled and received at least one application with the study device) will be used for analyses of safety and effectiveness endpoints. A Per-Protocol (PP) Population will neither be defined nor analyzed.

Clinical Trial Protocol ATM-2201	Version 2.0 28-Oct-2022	Confidential Page 6/25
-------------------------------------	----------------------------	---------------------------

SCHEDULE OF EVENTS AND PROCEDURES

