1 INTRODUCTION

Intralesional injection of corticosteroids is standard of care therapy for stubborn acne lesions. They are typically dosed with triamcinolone acetonide at concentrations of 0.5 mg/mL to 2.5 mg/mL (i.e., 0.5% to 2.5%) in volumes of 0.05 mL to 0.15 mL.

This proof-of-concept study will investigate the safety of using an intradermal needle adapter for delivery of intralesional triamcinolone injections in patients with acne vulgaris. The intradermal needle adapter is an accessory that slips on the end of a standard 32G 0.5" needle and reduces the effective length of the needle to 1mm. The adapter (currently a prototype) is made of biocompatible 304 Stainless Steel and is being developed to allow patients to safely self-inject triamcinolone, rather than depending on injections performed by a physician.

As intralesional triamcinolone injections are standard-of-care, the purpose of this proof-of-concept study is to test the safety of the intradermal needle adapter, not the safety and efficacy of triamcinolone per-se.

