2 STUDY OBJECTIVE

The objective of this proof-of-concept study is to investigate the safety of using an intradermal needle adapter for performing intralesional injections.

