9.4.1.1 Definition of Adverse Event

An AE is any untoward medical occurrence in a patient or clinical investigation subject administered a study device and which does not necessarily have a causal relationship with the study device. AEs include any unfavorable and unintended illness, sign, symptom, clinically significant laboratory test abnormality, or disease temporally associated with the use of a study device that has appeared or worsened during the course of the clinical trial, regardless of causal relationship to the study device under study.

The collection of non-serious AEs and serious adverse events (SAEs) will begin following the subject's signature of the informed consent form.

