9.4.1.2 Documenting Adverse Experiences

The PI is responsible to document all AEs that occur during the study. AEs should be documented as a single medical diagnosis. When this is not possible, AEs should be documented in terms of signs/symptoms observed by the PI or reported by the subject at each study visit. Each AE that appears to be independent of any prior event will be reported separately.

All AEs occurring after the subject signs the informed consent form through the last study visit must be reported, regardless of AE causality. All AEs, whether in response to a query, observed by the study site personnel, or reported spontaneously by the subject, will be recorded.

At each visit during the study, the subject will be assessed for the occurrence of new and ongoing AEs. The following data will be collected on all AEs and recorded on the appropriate CRF:

- Event name (diagnosis preferred, if unknown, record the signs/symptoms)
- Onset date and end date
- Maximum intensity (severity)
- Seriousness
- Action taken regarding study device
- Corrective treatment, if given

Clinical Trial Protocol ATM-2201	Version 2.0 28-Oct-2022	Confidential Page 16/25
-------------------------------------	----------------------------	----------------------------

- Outcome
- Investigator assessment of causality

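### The sole objective is the safety of a prototype adapter, but no planned item counts a malfunction without harm: adverse events are the only safety endpoint, and the injection videos have no criteria or analysis

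*Combined protocol and SAP*

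**What the plan says.** Section 2 gives a single objective: "The objective of this proof-of-concept study is to investigate the safety of using an intradermal needle adapter for performing intralesional injections". Section 1 says the purpose is to "test the safety of the intradermal needle adapter, not the safety and efficacy of triamcinolone per-se". It calls the adapter a prototype that "is being developed to allow patients to safely self-inject triamcinolone, rather than depending on injections performed by a physician". Section 8.1 describes a purely mechanical function: the adapter slips onto a 0.5 inch needle and "reduces the effective length of the needle to 1mm".

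The synopsis row "Safety Endpoints" contains one entry, adverse events. Section 9.4.1.1 begins its definition: "An AE is any untoward medical occurrence in a patient or clinical investigation subject administered a study device". The AE form in section 9.4.1.2 has one field about what was done with the device, "Action taken regarding study device", and it is completed only once an AE exists.

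On the injection itself, section 9.2.2.4 states "A video will be taken of each injected lesion starting from just prior to needle penetration"; filming ends up to 10 seconds after the needle is withdrawn. Section 9.3.2 collects injection pain on a visual analog scale (VAS) and rules that such pain is not an AE. Section 10 plans descriptive summaries of outcome variables, AE tables, disposition and a tabulation of deviations.

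**The concern.** What is under test is whether the adapter can be used safely, and its protective function is to hold a 12.7 mm needle (0.5 x 25.4) to 1 mm. If it loosens, leaks, lets the needle in further or fails to deliver, that bears directly on the objective whether or not this subject is hurt. Here the Investigator operates the device. A fault that is harmless in those hands is an early warning for the self-injection use described in section 1. Under the plan, such a fault has no predefined place in the data. A clean AE table could then be read as evidence about the adapter when it is evidence only about harm to about 20 subjects.

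**Working it through.** The documents give no malfunction rate, power or sample size calculation, so there is no stated figure to reproduce. The check has two parts.

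**1. Is there any route by which a harmless malfunction is counted?**

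- *AE reporting (9.4.1.1, 9.4.1.2, 10.2.1).* It needs a medical occurrence in the subject. A slip or leak without harm does not qualify, and the device field on the AE form is then never opened.
- *Schedule of events and visit procedures (9.1.1, 9.1.2).* Neither has an item for seating, leakage, depth, failed or repeated attempts, or completion without the adapter.
- *Protocol deviations (10.3.4, 11.3).* Section 6 says all enrolled subjects are treated with the device and section 8.2 specifies injection through it, so abandoning the adapter could be logged and tabulated as a deviation. Device failure is not a named category. A slip or leak during an otherwise compliant injection departs from no stated procedure.
- *Injection pain (9.3.2).* A painful fault may raise the VAS score, but the score does not identify the cause. A painless fault leaves no trace there.
- *Video (9.2.2.4).* It is a raw record of every injection, with no reader, criteria, CRF field or output.

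No route is defined to identify or count a malfunction without harm. In addition, section 10.3.1 limits the mITT population to subjects with at least one application of the device. Depending on how an application is read, a subject whose only attempt was abandoned could fall outside the analysis set.

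**2. How much could be missed? (illustration only)**

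Inputs: about 20 subjects (10.1) with 1 to 3 lesions each (8.2), so m = 20 to 60 injections. Assumed, with no basis in the documents: malfunction rate p = 10% per injection, and a fraction f = 5% to 20% of malfunctions that cause a reported AE. Injections are treated as independent. Direct recording is taken as complete (f = 1).

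P(at least one seen) = 1 - (1 - p x f)^m

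| m | Direct recording: 1 - 0.9^m | AEs only, f = 5%: 1 - 0.995^m | AEs only, f = 20%: 1 - 0.98^m |
|---|---|---|---|
| 20 | 88% | 10% | 33% |
| 40 | 98.5% | 18% | 55% |
| 60 | 99.8% | 26% | 70% |

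With p = 5% and m = 40, the contrast is 1 - 0.95^40 = 87% against 10% (1 - 0.9975^40) to 33% (1 - 0.99^40).

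Direct recording has its own limit. With no malfunction in any of 20 subjects, the exact two-sided 95% upper bound is 1 - 0.025^(1/20) = 16.8%.

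**The case against.** A reader might infer that malfunctions are recorded nowhere. The documents do not support that. Abandonment can reach the final report as a deviation, a painful fault may show on the VAS, and photographs are taken before and after injection (9.2.2.5). The video is a study record, and section 9.2.2 lists videography among the methods by which each injected lesion is to be assessed. This part of the objection stands. What survives it is narrower: these routes are incidental, and none covers a painless slip or leak in a countable form.

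A reader might also infer that the video would reveal every fault. That is unsupported too. No angle or magnification is specified, depth of entry lies under the skin and the adapter, and installation before filming and leakage after it fall outside the recording. Video can support only what is externally visible.

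The probabilities rest on assumed rates. Independence ignores clustering of lesions within subjects, and complete capture flatters direct recording. They show direction and rough scale, not an estimate.

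Finally, malfunction without harm could be called performance rather than safety, and the plan has no hypothesis test or success criterion (10, 10.3.7) that a missed fault would tip. It is therefore too strong to say the study will reach a falsely favourable conclusion. But when the stated subject is the safety of using a device that works by limiting needle length, whether it held that limit belongs at least in the descriptive results.

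**Conclusion.** The point holds in this form: AEs are the only safety endpoint, no predefined item identifies or counts a malfunction without harm, and the filmed injections have no planned assessment. Followed as written, the study could report no safety findings despite repeated malfunctions. That conclusion comes from the plan's own objective, AE definition and procedures, and does not depend on the illustrative rates. Under the stated assumptions, with 10% malfunction, the AE-only plan would miss every malfunction with probability 30% to 90% across 20 to 60 injections (one minus 70% and one minus 10%). Direct recording would miss them all with probability at most 12%. The study is feasible without the change, but its single objective is only partly measured, so the change should be made.

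**What to change.** Add a short per-lesion device-performance form at Visit 1, completed by the Investigator at the time of injection, with yes/no items:

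- adapter stayed seated;
- injection completed through the adapter;
- visible leakage or backflow;
- apparent entry beyond the stop;
- adapter replaced or abandoned.

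Use the existing video as supporting evidence for the externally visible items only, not for entry depth.

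Report any device malfunction descriptively next to AEs: per subject with number, percentage and exact 95% CI, and per injection with number and percentage. Count every subject in whom use of the adapter was attempted, so that an abandoned attempt stays in the denominator.

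The cost is one CRF page, one table and a few minutes per subject. The visit, the Investigator and the video are already in the plan. The safety summary may look less favourable.

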9.2.2.5 Target Lesion Photography

Photographs will be taken at each study visit of each injected inflammatory lesion. At Baseline, photographs will be taken both pre- and post-injection.

9.3 Subject Assessments

9.3.1 Target Lesion Pain

For each inflammatory lesion to be injected, lesion pain will be self-assessed by the subject using a 10 cm Visual Analog Scale (VAS) Pain Scale. Lesion pain at Baseline will be recorded prior to injection(s). The occurrence of inflammatory lesion pain is expected and will not be considered an AE.

9.3.2 Intralesional Injection Pain

Injection pain will be self-assessed at each study visit by the subject using the Visual Analog Scale (VAS). Lesion pain at Baseline will be recorded prior to injection(s). Injection Site Pain during injection will be assessed for all injected lesions immediately after the final lesion has been injected. Ten (10) minutes after these assessments, injection pain will be assessed again for all injected lesions. The occurrence of injection site pain is expected and will not be considered an AE.

Clinical Trial Protocol ATM-2201	Version 2.0 28-Oct-2022	Confidential Page 15/25
-------------------------------------	----------------------------	----------------------------

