9.4 Safety

9.4.1 Adverse Events

All observed or volunteered AEs regardless of suspected causal relationship to the study device will be recorded in the CRF. Subjects will be questioned for the occurrence of any new or worsening signs or symptoms at each visit.

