9.4.1.3 Serious Adverse Events

All AEs will be assessed as either serious or non-serious.

An SAE is defined as any untoward medical occurrence that at any dose:

- Results in death
- Is immediately life threatening, (the term "life threatening" in the definition of "serious" refers to an event in which the subject is at risk of death at the time of the event; it does not refer to an event which hypothetically might have caused death if it were more severe)
- Requires inpatient hospitalization or prolongation of existing hospitalization (hospitalization for elective surgery for a baseline condition is not considered an AE)
- Results in persistent or significant disability/incapacity (permanent or substantial disruption of a person's ability to conduct normal life functions)
- Is a congenital anomaly/birth defect
- Is a medically important event that may not be immediately life threatening or result in death or hospitalization but may jeopardize the subject and may require medical or surgical intervention to prevent one of the above listed outcomes. Examples of such events include, but are not limited to, allergic bronchospasm requiring intensive treatment in an emergency room or at home; blood dyscrasias or convulsions that do not result in inpatient hospitalization.

Note: A spontaneous abortion will be considered an SAE and must be reported per Reporting of SAEs under Section 9.4.1.6.

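### The exemption of lesion and injection-site pain from adverse events has no stated upper limit, so isolated severe pain could be missing from the AE tables of a study whose only listed safety endpoint is AEs

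*Combined protocol and SAP*

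**What the plan says.** - **Objective and endpoint.** Section 2 gives one objective, to "investigate the safety of using an intradermal needle adapter for performing intralesional injections". In the Synopsis, the row "Safety Endpoints" lists adverse events and nothing else.
- **Exemptions.** Section 9.3.1: "The occurrence of inflammatory lesion pain is expected and will not be considered an AE". Section 9.3.2: "The occurrence of injection site pain is expected and will not be considered an AE". Neither is limited by intensity, duration or seriousness, and neither cross-refers to Section 9.4.
- **General AE rules.** Section 9.4.1: "Subjects will be questioned for the occurrence of any new or worsening signs or symptoms at each visit". Section 9.4.1.1 counts as AEs those unfavourable symptoms "temporally associated with the use of a study device that has appeared or worsened during the course of the clinical trial, regardless of causal relationship". Section 9.4.1.2 lists what is recorded for each AE, including maximum intensity, seriousness, corrective treatment, outcome and "Investigator assessment of causality". It also prefers a single diagnosis to separate symptoms.
- **SAE rules.** Section 9.4.1.3: "All AEs will be assessed as either serious or non-serious". The SAE definition that follows is framed around untoward medical occurrences, not around AEs. Section 9.4.1.6 requires every SAE to be reported, whether or not it is related to the device.
- **Analysis.** Section 10.2.1 tabulates AEs by severity and by relationship to the device. Section 10 summarises all outcomes descriptively, with range and two-sided 95% CIs.
- **Other records of pain.** Lesion pain is rated on a VAS at all six visits (Schedule of Events). Injection pain is rated just after the last injection and again 10 minutes later (Section 9.3.2). Concomitant treatments are entered in the CRF (Section 7.1).

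**The concern.** Pain where the needle enters is a plausible effect of a needle accessory. Section 1 describes this one as a prototype being developed so that patients can inject themselves. Calling some pain expected is a good reason not to record every routine twinge as an AE. It is not a reason to exempt pain of any intensity.

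If the investigator applies the two sentences as written, a subject whose only problem is severe isolated pain would add nothing to the AE rate, the severity table or the relatedness table, and those tables are the study's stated safety result. The investigator also has no statement that the exemption leaves SAE reporting intact.

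**Working it through.** The plan gives no rate, power or target for AEs, and about 20 subjects are declared without a formula (Section 10.1). There is therefore no figure to reproduce. The check is mainly of text, followed by an illustration of scale.

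**Step 1. Does anything in Section 9.4 cap the exemption?** No. Sections 9.4.1 to 9.4.1.6 do not mention it. The definition in Section 9.4.1.1 covers symptoms that appear or worsen, so worsening or severe pain after the injection meets it. The specific sentences in Sections 9.3.1 and 9.3.2 say that pain is not an AE. The documents do not say which governs.

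**Step 2. What follows if the specific sentences govern?** Section 10.2.1 builds its tables from AEs, so exempt pain cannot enter them. The fields in Section 9.4.1.2 are collected for AEs, so exempt pain has no seriousness, outcome or causality entry.

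**Step 3. What do the other records carry?**

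| Record | What it shows for isolated pain | What it is not specified to show |
|---|---|---|
| VAS (Sections 9.3.1, 9.3.2, 10) | Score at set times; a high score appears as the maximum | AE severity grade, seriousness, outcome, causality; no VAS cut-off for severe pain is given |
| Concomitant treatment (Section 7.1) | Name of the treatment and end date | Seriousness, outcome or causality of the pain |
| AE under another diagnosis (Section 9.4.1.2) | All AE fields, where pain belongs to a diagnosed complication such as infection | Nothing for isolated pain |

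**Step 4. Is serious pain reportable?** The breadth of the SAE definition and the duty to report all SAEs point to yes. The sentence applying the seriousness assessment to AEs, together with the statement that pain is not an AE, points the other way. The text is ambiguous; it does not exclude reporting.

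**Step 5. Scale.** Inputs: n = 20 (Section 10.1, taken as the number treated); 95% two-sided intervals (Section 10). The plan names no interval method, so the exact Clopper-Pearson interval is used here.

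- One subject: 1/20 = 5 percentage points.
- 0/20: upper limit = 1 − 0.025^(1/20) = 16.8%; interval 0 to 16.8%.
- 1/20: lower limit = 1 − 0.975^(1/20) = 0.1%; upper limit = 97.5th percentile of Beta(2, 19) = 24.9%.
- 2/20: 10% (1.2 to 31.7%). 3/20: 15% (3.2 to 37.9%).

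Each row with at least one event is what the table would show if that many subjects with isolated severe pain, and no other AE, were counted. With the exemption applied literally, all of them would read 0/20.

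The chance that at least one of 20 subjects is affected is 1 − (1 − p)^20. The rates p are assumptions, since the documents give none: 64% at p = 5%, 88% at p = 10% and 98.8% at p = 20%.

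**The case against.** The best case for the plan is that pain is captured separately by design. It is solicited lesion by lesion on a VAS and summarised with range and confidence intervals, which is more systematic than spontaneous AE reporting. The exempting sentences speak of the occurrence of expected pain, and Sections 9.4.1 and 9.4.1.1 still bring in new or worsening symptoms. An investigator could therefore reasonably record unexpectedly bad pain as an AE. In a single-arm study, a judgement that pain is device-related cannot separate the adapter from the needle or the injectate. There is no hypothesis test or AE-rate success criterion that a shift from 0/20 to 1/20 would overturn.

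Much of this stands, and it rules out several stronger readings that a reader might infer:

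- **That pain data are lost.** They are not; the VAS and treatment records remain. Under the COVID-19 contingency in Appendix B, the lesion-pain VAS cannot be collected remotely. That is a side issue: in-person visits are preferred, and AEs and medications are still reviewed remotely.
- **That every subject with severe or treated pain drops out of the AE rate.** Pain that belongs to a diagnosed complication is an AE under that diagnosis.
- **That serious pain is exempt from SAE reporting.** The documents leave this unclear and do not exclude it.
- **That the exemption plainly overrides the AE definition.** The two conflict, and neither is said to prevail.

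What the objection does not answer is the literal reading for isolated severe pain. The VAS carries no causality, seriousness or outcome and is not listed as a safety endpoint. Descriptive status does not help either, because the AE description is itself the stated safety result.

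**Conclusion.** The point holds in a limited form. Sections 9.3.1 and 9.3.2 exempt pain without an upper limit, conflict with Section 9.4.1.1 for pain that worsens, and leave SAE handling unclear. Followed literally, they keep isolated severe pain out of the severity and relatedness tables and leave it without an AE record.

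The size is unknown. Each omitted subject is worth 5 percentage points if 20 are treated; the contrast of 0/20 with 1/20 is an illustration that assumes one affected subject and no other AE. The conclusion rests on the literal reading of the two sentences, which the text permits but does not compel. It should be corrected because it touches the study's only listed safety endpoint and the correction is cheap. It does not invalidate the design.

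**What to change.** Reconcile Sections 9.3.1 and 9.3.2 with Sections 9.4.1.1 to 9.4.1.6. Keep the exemption for ordinary expected pain and add to both sections a sentence such as: *This exemption does not cover pain that is serious under Section 9.4.1.3 or severe under Section 9.4.1.4, and it never overrides SAE reporting under Section 9.4.1.6.* Whether moderate or treated pain is also recorded as an AE is for the sponsor to decide and state. A bare treatment criterion would have no floor, since any minor remedy for mild pain would then create an AE.

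Report the existing injection-pain VAS, immediate and at 10 minutes, alongside the AE tables as part of the safety results.

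The cost is protocol wording, a few more AE entries and a possibly less favourable AE rate. No visits, subjects or measurements are added.

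Section 9.3.2 also places injection-pain ratings at every visit, while the Schedule of Events and Section 9.1 place them at Visit 1 only. That conflict needs reconciling as a separate matter and adds no weight to this point.
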